“A research study in which one or more human subjects are prospectively assigned to one or more interventions. An “intervention” is defined as a manipulation of the subject or subject’s environment for the purpose of modifying one or more health-related biomedical or behavioral processes and/or endpoints. Examples include: drugs/small molecules/compounds; biologics; devices; procedures (e.g., surgical techniques); delivery systems (e.g., telemedicine, face-to-face interviews); strategies to change health-related behavior (e.g., diet, cognitive therapy, exercise, development of new habits); treatment strategies; prevention strategies; and, diagnostic strategies (which may include placebo or other control) to evaluate the effects of those interventions on health-related biomedical or behavioral outcomes.”

Use the following four questions to determine the difference between a clinical study and a clinical trial:

- 1) Does the study involve human participants? Yes No
- 2) Are the participants prospectively assigned to an intervention? Yes No
- 3) Is the study designed to evaluate the effect of the intervention on the participants? Yes No
- 4) Is the effect being evaluated a health-related biomedical or behavioral outcome? Yes No

Note that if the answers to the 4 questions are yes, your study meets the NIH definition of a clinical trial, even if...

- You are studying healthy participants
- Your study does not have a comparison group (e.g., placebo or control)
- Your study is only designed to assess the pharmacokinetics, safety, and/or maximum tolerated dose of an investigational drug
- Your study is utilizing a behavioral intervention

If yes to all 4 questions, please confirm that the research team is familiar with and agrees to comply with the investigator requirement to register the study on the ClinicalTrials.gov database. Additionally, the approved consent document(s) must be uploaded to the ClinicalTrials.gov database Yes No

For any assistance with registration of your trial or the requirements, please contact [contact]

PROTOCOL TITLE: Keeping rural minority ‘essential’ workplaces open safely during the COVID-19 pandemic: The role of frequent point-of-care molecular workplace surveillance for miners

Table of Contents

1. Objectives	5
2. Background	6
3. Study Design	8
4. Inclusion and Exclusion Criteria	11
5. Number of Subjects	11
6. Study Timelines.....	11
7. Study Endpoints:	12
8. Research Setting.....	13
9. Resources Available	14

The *long-term goal* of the study is to mitigate the spread of the pandemic in miners, a population of high-risk, rural essential workers who are susceptible and vulnerable to COVID-19, partly based on exposure to particulate air pollution, and who are predominantly racial/ethnic minorities in New Mexico (NM) (3, 11). The study *objective* is to provide proof-of-principle for frequent point-of-care molecular testing as a workplace surveillance tool to monitor and prevent the spread of SARS-CoV-2 infection in this unique population. The *central hypothesis* is that frequent workplace molecular surveillance is an effective method to reduce SARS-CoV-2 infection and discover novel host risk factors for the virus. The site of molecular surveillance (intervention site) will be a surface coal mine in McKinley County, NM, located just outside the Eastern Agency of the Navajo Nation, comprised of 66% minority miners. This site offers a unique opportunity for a community-based study of SARS-CoV-2 infection in this population. Miners at the intervention site will provide nasal swabs before beginning their work shift on alternate days that will be analyzed with a ‘screening’ molecular test (12). This test is ideal because it is low cost, simple, portable, point-of-care, rapid, and can be performed by minimally trained professionals in low-infrastructure settings. The control site is a similar coal mine in Campbell County, Wyoming (WY). Both mines, operated by the same company, have similar engineering, administrative, and personal protective measures in place. The *rationale* for this study is to establish the suitability of longitudinal molecular surveillance to prevent and control SARS-CoV-2 infection in this unique population by completing the following specific aims.

Specific Aim 1: To determine the acceptance rate to frequent point-of-care molecular workplace surveillance among miners. *Hypothesis 1:* Miners will have a cumulative acceptance rate of frequent testing at $\geq 85\%$, with the added objective of exploring difference in acceptance by miner characteristics.

Specific Aim 2: To determine the ability to detect the presence of SARS-CoV-2 by point-of-care molecular workplace surveillance in a real-world setting of miners.

Hypothesis 2: The sensitivity of the screening test in a real-world study setting is a) comparable to that described by others in controlled settings, and b) positively associated with viral load in upper respiratory specimens (latter measured in nose and nasopharynx using quantitative reverse transcriptase-polymerase chain reaction or RT-PCR).

Specific Aim 3: To determine the effectiveness and implementation costs of frequent point-of-care molecular workplace surveillance on reducing incident infection rates of SARS-CoV-2.

Hypothesis 3A: Frequent point-of-care molecular testing over up to twelve months in the intervention mine will result in lower incident seropositivity rates compared to the control mine. *Hypothesis 3B:* Frequent point-of-care molecular surveillance in the intervention mine is cost-effective compared to the control mine.

Specific Aim 4: To determine novel predictive factors associated with incident SARS-CoV-2 infection, tests, and vaccination in miners. *Hypothesis 4A:* Miners with incident infection demonstrate less frequent use of cloth face-coverings outside the workplace, greater mine dust exposure intensity, presence of dust-related lung

PROTOCOL TITLE: Keeping rural minority ‘essential’ workplaces open safely during the COVID-19 pandemic: The role of frequent point-of-care molecular workplace surveillance for miners

disease, and racial/ethnic minority status than those not infected. *Hypothesis 4B:* Test and vaccine uptake by miners is predicted by specific barriers and facilitators.

Hypothesis 4B involves a separate but related study, titled “Facilitators and barriers for COVID-19 testing uptake and its impact on vaccine uptake in a rural diverse essential workplace ([name]/[name], Co-PIs; NIH 1U23MD016258-01 RADx-UP Central Data Coordination Center Rapid Research Pilot Project)”. The objective is to determine facilitators and barriers to COVID-19 test uptake, and the impact of the latter on vaccine uptake, at a surface coal mine. This study involves the administration of a questionnaire once between 6 and 12 months time point.

2. Background

Coronavirus disease 2019 (COVID-19), caused by the severe acute respiratory syndrome-related coronavirus-2 (SARS-CoV-2) infection, is a novel disease, frequently transmitted at the workplace. Rural workers are increasingly affected, particularly racial/ethnic minorities (1-3). In New Mexico (NM), a rural, minority-majority, and medically underserved state, the greatest impact from COVID-19 is seen in McKinley County, in and around the Navajo Nation. The high risk of infection in minority communities could be due to genetic factors, immunological differences, social determinants of health (4), comorbidities, and/or high prevalence of concomitant co-exposures (1, 5, 6), in alignment with COVID-19 known risk factors (7-10). Despite sentinel studies in health care workers, meatpackers, and cruise ship workers, there are limited studies on the spread of SARS-CoV-2 infection in rural essential workers with health disparities. This critical *gap-in-knowledge* must be addressed to develop and implement novel pandemic strategies to keep rural minority essential workplaces open, particularly in environments such as coal mines, which are unable to use physical distancing, flexible schedules, or telecommuting interventions (3).

Scientific Premise

Essential workers: An estimated 15 million US workers provide essential services during the pandemic. ‘Essential’ services are deemed critical to societal infrastructure and are crucial for rural economies. Initial reports have highlighted the risk imposed on health care workers during the pandemic. However, essential work extends beyond health care. Despite being categorized as essential, many rural workers have not been adequately tested and studied for SARS-CoV-2 infection (13). Miners are rural essential workers with

Table 1: SARS-CoV-2 infection vulnerability and susceptibility factors in miners	
Vulnerable workers: Workers at higher risk due to the greater likelihood of increased exposure	Susceptible workers: Workers at higher risk (or worse outcomes) at any level of exposure
Hazardous work characteristics: 
 Exposure to infected aerosols amongst essential workers unable to work from home Enclosed, or poorly ventilated workplaces; difficulty distancing from virus-laden aerosols Prolonged and close face-to-face or physical contact Lack of access to flexible work schedule 	Demographic characteristics: 
 Male sex Rural residence American Indian & Hispanics (particularly in intervention mine) Co-morbidities: 
 Obesity, hypertension, diabetes mellitus, cardiovascular disease Co-exposures: 
 Smoking/environmental tobacco smoke Work in high particulate air pollutant environments
Cross-cutting factors for vulnerable and susceptible workers	
Enhanced Exposure to SARS-CoV-2: 
 Residence in homes that are overcrowded or multigenerational or without access to running water use (particularly in intervention mine) Predisposition to Poorer Health Outcomes: 
 Low socioeconomic status 	

PROTOCOL TITLE: Keeping rural minority ‘essential’ workplaces open safely during the COVID-19 pandemic: The role of frequent point-of-care molecular workplace surveillance for miners

multiple vulnerability and susceptibility factors, as noted in Table 1, making them a unique population to test and study.

Table 2. Characteristics of NM miners (n=6685)

Characteristic	%
Male	97
Race/ Ethnicity	
Non-Hispanic white	28
Hispanic	37
American Indian	33
Age (years)	
< 40	14
40-59	44
≥60	42
Smoker	
Never	47
Former	35
Current	19
Self-Reported Diseases (n=5281)	
Chronic bronchitis	32
Current asthma	5
Dust-related lung disease	6
Cardiovascular disease	18
Diabetes mellitus	13

efforts.

Table 3: Research attitudes in American Indian (n=112; Group 1) and non-American Indian miners (n=47; Group 2). Data from town hall meetings.

Question: How would you feel about....	Gp.	Yes, %	Maybe, %	No, %	P value
Participate in a long-term research study?	1	48.2	41.1	10.7	0.5
	2	38.3	48.9	12.8	
Provide blood samples for research?	Gp.	Comfortable	No feeling	Un-comfortable	0.14
	1	60.7	16.1	23.2	
Long-term storage of biospecimens?	2	63.8	29.8	6.4	0.02
	1	47.3	21.4	31.3	
	2	63.8	23.4	12.8	

miners are at greater risk for developing lung disease than non-Hispanic white miners (18, 22). The sex, race/ethnicity, and smoking distribution, and prevalence of lung and cardiovascular diseases, diabetes, and hypertension support our position that miners are a unique population for studying SARS-CoV-2.

The literature indicates that American Indians are reticent towards participating in research due to historic mistrust, resulting in some of the poorest health outcomes of any racial/ethnic group (21). However, our data from town hall meetings (Table 3) indicate that American Indian miners welcome participation in research to the same degree as those of non-American Indian descent, but maybe less comfortable with sharing biological specimens. To address this challenge, we will not store biological specimens for future research without consent for the same.

Community partners: Our engagement with key mining community stakeholders provides the *foundation* for the proposed project as well as *sustainability* for future partnerships. Our mobile screening program for NM and WY miners (14) was recognized as an innovation at the HRSA Rural Health Information Hub (Fig. 1). We have co-authored multiple research manuscripts with our partners (3, 15-20). Our Mining Advisory Council (MAC), chaired by a partner ([name], LOS) allows stakeholders to review research materials and protocols. Our Miners’ Wellness TeleECHO Program helps telementor rural professionals caring for miners (21), details for which are available at <http://echo.unm.edu/miners-wellness/>. The Advisory Council and the TeleECHO Program, recognized as rural COVID-19 innovations by HRSA’s Rural Health Information Hub, exemplify our partnerships that will be leveraged for future pandemic mitigation

Figure 1: HRSA-funded mobile screening clinic for NM & WY miners, operated by NM & WY Black Lung Programs.

Based upon data shown in Table 2, we serve 37% Hispanic, and 33% American Indian miners in NM, indicating robust participation from populations historically underrepresented in health research. NM data (19) indicate that minority

PROTOCOL TITLE: Keeping rural minority ‘essential’ workplaces open safely during the COVID-19 pandemic: The role of frequent point-of-care molecular workplace surveillance for miners

In a 2016 study at the intervention mine, we determined that 58% of miners used social media, 91% reported Internet access over their telephone, and 92% used the phone for texting. Miners reported using social media for 51 (mean) \pm 142 (SD) minutes daily for 6 \pm 5 years, indicating adept and frequent usage. 52% of those surveyed indicated an interest in using social media to receive information about miners’ projects from our group. The social media-savvy nature of rural NM miners, initially surprising to our group, is a novel way to reach out to the study population using phone/web apps, which will be developed by Ingenuity Software Labs, Albuquerque, New Mexico. Our mine safety officer partner, [name], CMSp, helped establish our social media engagement and education plan, including a video tutorial.

[figure not shown]
Table 4: List of study SARS-CoV-2 tests

SARS-CoV-2 test	FDA authorized
Screening test (molecular)	Yes
Diagnostic test (RT-PCR)	Yes
Serologic antibody test	Yes
Viral burden (Quantitative RT-PCR or RT-qPCR)	Research test

Our capacity for SARS-CoV-2 testing: Molecular tests help establish a diagnosis by detecting SARS-CoV-2 nucleic acids using RT-PCR or nucleic acid amplification assays (23). Laboratory-based RT-PCR assays performed on nasopharyngeal (NP) swabs collected by trained professionals (i.e., diagnostic test) are the cornerstone of diagnostic testing. A recent study showed that unsupervised, self-collected, midnasal swabs for the

detection of SARS-CoV-2 are comparable to clinician-collected nasopharyngeal swabs (Cohen K statistic = 0.81), offering a unique opportunity to scale-up workplace testing (24). The commercial choice of screening test for our study will be finalized, based on test availability, in collaboration with the NIH RADx-UP initiative, but will have the following characteristics (Regulatory status: All; Diagnostic target: Viral antigen; Analysis location: Self or Lab CLIA Waived; Platform: Lateral flow; Specimen collected: Nasal swab; Company: Any; Minutes to result: 30 minutes or less; Sensitivity and specificity: At least 80%)..

We have performed over 600 RT-qPCR measurements of patient samples for our ongoing projects using the CDC N1 and N2 assays and a published “Wuhan” spike protein (S) gene assay. The results showed that the CDC N1 assay is the most robust. As such, we present viral load dynamics (\log_{10} copies/mL) for the N1 assay in non-severe (n=13) and severe (n=19) patients with COVID-19. As shown in Fig. 2, patients with severe disease have a higher and more protracted viral load in the upper respiratory tract (NP, $P<0.001$, panel A) and peripheral whole blood ($P<0.01$, panel B) compared to non-severe patients. Also, to capture viral load during the time-course measurements, area-under-curve (AUC) was calculated for the two groups. Patients with severe disease had a higher AUC than those with non-severe disease for both NP and peripheral blood (Fig. 3C). There was a significant positive relationship between severe disease and viral loads measured from the NP swabs ($P=1.2\times 10^{-4}$) and whole blood ($P=4.9\times 10^{-3}$), and between the NP and peripheral blood viral loads ($P=2.5\times 10^{-6}$).

3. Study Design

3.1. Specific Aim 1:

Frequent testing (i.e. alternate work shifts) using less sensitive molecular tests is proposed to keep workplaces open safely during the pandemic (26, 27), but its feasibility has not been studied. Our *objective* is to perform an experimental feasibility study to determine the acceptance of frequent point-of-care screening testing in our unique population. Our working *hypothesis* is miners will have a cumulative acceptance rate of frequent screening testing at $\geq 85\%$, with the added objective of exploring difference in acceptance by miner characteristics. The *rationale* for the proposed work is to establish worker acceptability for the proposed workplace surveillance. We expect that our findings will help design novel primary SARS-CoV-2 prevention strategies at rural workplaces, including future vaccination studies of essential workers.

Research design: This is a longitudinal surveillance study over up to twelve months, starting January 2021. We will utilize a fixed cohort of less than 250 at-risk miners at the intervention site, a surface coal mine in McKinley County, NM, with a population comprised of 66% minorities (American Indian and Hispanic), in partnership with the mine leadership.

3.2. Specific Aim 2:

Effective molecular surveillance may be only marginally affected by a test’s lower analytical limits of detection (26). Although molecular tests may show false negatives (FN) early on or late in the infection cycle when viral load is increasing and decreasing, respectively, the viral burden corresponding to a positive screening test is not established (29). Interim results demonstrate that when compared to the diagnostic (laboratory-based qualitative RT-PCR), screening test in controlled settings (in urgent care clinic, hospitalized and nursing home patients) is $\geq 95\%$ sensitive and $\geq 99\%$ specific (30). In our study, the screening test utilizes samples collected: a) at the workplace, b) by the participant, c) using nasal swabs followed by point-of-care testing, d) in a low infrastructure community setting, e) by minimally trained professionals. The screening test was granted emergency use authorization without a detailed study on end-user needs in the real-world, but each of the above variables introduces a potential source of error in results.

PROTOCOL TITLE: Keeping rural minority ‘essential’ workplaces open safely during the COVID-19 pandemic: The role of frequent point-of-care molecular workplace surveillance for miners

Our *objective* is to determine the ability of the screening test to correctly detect the presence of the virus in upper respiratory specimens in the real-world setting. This will be accomplished by evaluating screening test performance at the workplace by quantifying viral loads from self-collected nasal swab and health personnel-collected nasopharyngeal (NP) swab specimens, using quantitative RT-PCR (RT-qPCR). Our *working hypothesis* is that the sensitivity of the screening test in a real-world study setting is a) comparable to that described by others in controlled settings, and b) positively associated with viral load in upper respiratory specimens. Successful completion of this study will help determine the real-world performance of less sensitive screening tests in disease settings of mild severity.

Table 5: Test findings studied in Aim 2

Measurement	Biological specimen	N	Purpose
Screening test (qualitative)	Self-collected nasal swab	less than 250	Workplace surveillance
Diagnostic test RT-PCR (qualitative)	Healthcare personnel collected NP swab	less than 250	Establish sensitivity, specificity & diagnostic accuracy of screening test
Quantitative RT-PCR	Self-collected nasal swab	less than 250	Quantitate viral load vis-à-vis screening test
Quantitative RT-PCR	Healthcare personnel collected NP swab	less than 250	Quantitate viral load vis-à-vis screening test
Sputum biomarkers	Spontaneous home sputum samples	Less than 250	Quantitate inflammation

Research design: In this cross-sectional study, sensitivity, specificity and diagnostic accuracy (31) of the screening test on a self-collected nasal swab will be established by comparison with diagnostic test (qualitative RT-PCR), the latter conducted on an NP swab collected on the same day by trained health personnel, in a CLIA certified clinical laboratory (TriCore; Table 5). Also, since the diagnostic test is qualitative, we will also quantify viral load (\log_{10} copies/mL) from repeat nasal (self-collected) and NP (collected by healthcare personnel) swab specimens using RT-qPCR established in the [name] research laboratory (32). Viral load will be determined with primers and probes (N1 and RP) using the CDC 2019-nCoVEUA-01 diagnostic panel (33). Miners with any positive screening test (plus a sample of ~200 miners with a negative test) will undergo the above testing procedures. Database management and timelines will be similar to those described in Aim 1.

3.3. Specific Aim 3:

The role of frequent point-of-care molecular workplace surveillance to monitor and prevent the spread of SARS-CoV-2 is inadequately studied, particularly in rural essential workplaces. Our *objective* is to examine the effectiveness and costs of frequent point-of-care molecular workplace surveillance in rural essential workers. Our *working hypothesis 3A* is that frequent point-of-care molecular testing over up to twelve months in the intervention mine will result in lower incident seropositivity rates compared to the control mine. *Hypothesis 3B* is that frequent point-of-care molecular surveillance in the intervention mine is cost-effective compared to the control mine. The *rationale* for the

PROTOCOL TITLE: Keeping rural minority ‘essential’ workplaces open safely during the COVID-19 pandemic: The role of frequent point-of-care molecular workplace surveillance for miners

proposed work is that by establishing its effectiveness, implementation costs, and cost-effectiveness, our study will increase the real-world utility of workplace molecular testing, resulting in a novel primary prevention strategy targeted at rural essential workers.

Research design: We will conduct a up to twelve-month longitudinal surveillance study of miners at the intervention site (n=less than 250) in McKinley County, NM, and control site (n=less than 350) in Campbell County, WY. Both surface coal mines, operated by the same company, have similar engineering, administrative, and personal protective measures in place, including SARS-CoV-2 symptom & fever screening. While there will be frequent point-of-care molecular testing at the intervention site, seropositivity (baseline, 3, 6, and approximately12 m) will be measured at both sites.

3.4. Specific Aim 4:

Factors impacting SARS-CoV-2 spread is not well studied in rural essential workers outside healthcare. Our *objective* is to examine novel factors affecting the spread of infection in miners. A recent epidemiological study reported high COVID-19 mortality in communities exposed to ambient particulate air pollution (11). This novel risk factor is relevant for miners who are exposed to high levels of particulate air pollution at the workplace. Further, although the CDC encourages the public use of a cloth face-covering, its use by miners may vary, based upon individual and community factors (38), and has not been adequately studied. Our working *hypothesis 4A* is that miners with incident infection demonstrate less frequent use of cloth face-coverings outside the workplace, greater mine dust exposure intensity, presence of dust-related lung disease, and racial/ethnic minority status than those not infected. *Hypothesis 4B:* Test and vaccine uptake in miners is predicted by specific barriers and facilitators. The *rationale* for the proposed work is to prevent the spread of COVID-19 infection. We expect that our findings will result in novel primary prevention strategies for workers in dusty trades.

Research design: This is a up to twelve-month longitudinal surveillance study at the intervention (n=less than 250) and control (n=less than 350) mines.

4. Inclusion and Exclusion Criteria

All miners will be recruited at the mine site with the support of mine leadership.

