Power calculations: If we recruit less than 250 miners, we have the power to estimate 85% acceptance rate \pm 4.6%. For a comparison of acceptance rates between predictor groups, we assume, for example, non-Hispanic white and minority miners (1/3 and 2/3 of the study population respectively) have 85% and 80% acceptance respectively. We used simulation to assess power for Poisson regression analyses where the rate denominator (offset) is the number of miner workdays, assumed to be 95% of possible days. For these conditions, power is 94% for a 5% lower acceptance rate for minority miners. We also used simulation to assess the planned longitudinal analysis of miner acceptance by assuming that miners attended work 95% of the shifts, that initial acceptance is 85% and that there is a linear decline in acceptance over the study to a final acceptance rate of 80%. For repeated measures on about 200 miners, the power to detect a linear decrease to 80% is 95%.

13.2. Specific Aim 2:

Statistical analysis: We will compare screening test performance measures between our real-world study setting and controlled settings (as published by others). We will use a one-sample Exact test for a binomial proportion to test whether sensitivity for the screening test is the same as that published. We will correlate screening test results with quantitative viral loads, and perform Bland-Altman plots to reveal systematic differences between viral loads collected by the two sampling methods.

Power Calculations: If we conservatively estimate identifying 25 true positive miners, using a one-sample Exact test for a Binomial proportion equal to the comparison test, we have the power (>90%) to detect a difference between the screening and the comparison test if the screening test sensitivity is 90% or lower.

13.3. Specific Aim 3:

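### The screening test is labelled molecular but specified as a not-yet-chosen lateral-flow antigen test, and Hypothesis 2a has no numeric null tied to it

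*Combined protocol and SAP*

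**What the plan says.** **The label.** The title, the objectives and Aims 1 to 3 speak of molecular surveillance or testing. Section 1 says the swabs will be analysed with a "screening’ molecular test (12"), and Table 4 lists "Screening test (molecular"). Section 2 also says what the term means: "Molecular tests help establish a diagnosis by detecting SARS-CoV-2 nucleic acids using RT-PCR or nucleic acid amplification assays (23").

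**The specification.** The same paragraph of section 2 lists the characteristics the chosen product will have. They include "Diagnostic target: Viral antigen", "Platform: Lateral flow" and "Sensitivity and specificity: At least 80"%. Sections 2 and 12.1 both leave the product to be settled later, with advice from the NIH RADx-UP programme.

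**The benchmark.** Section 3.2 reports interim results in which the "screening test in controlled settings (in urgent care clinic, hospitalized and nursing home patients) is" at least 95% sensitive and at least 99% specific. Hypothesis 2a is that real-world sensitivity is comparable with what others found in controlled settings. Section 13.2 plans a one-sample exact binomial test "to test whether sensitivity for the screening test is the same as that published". It gives no numeric null, alpha or sidedness for this test. It states power above 90% with 25 true positives if sensitivity is 90% or lower, against a proportion equal to that of the comparison test, again without a number.

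**The concern.** By the plan's own account of the word, a lateral-flow test for viral antigen is not molecular. If the plan is followed as written, its acceptance, effectiveness and cost results will be reported as findings about molecular surveillance, although the specification admits only antigen tests. That is an error about what the intervention is, not a missing detail.

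For Hypothesis 2a the uncertainty also affects the analysis. The conclusion depends on the null, and the null depends on which test is meant. The documents offer a selection floor of 80%, a cited figure of at least 95%, and a power statement that must have used something else. With no number fixed, the null could be settled after the Aim 2 data are seen. A rejection could also reflect a benchmark taken from a different test as easily as a loss of performance at the mine.

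**Working it through.** **Inputs.** From 13.2: n = 25 true positives, sensitivity under the alternative 90%, stated power above 90%. From 3.2: the cited controlled-setting sensitivity, at least 95%, taken here as 95%. From section 2: the floor of 80%. Assumed, because 13.2 is silent: two-sided alpha 0.05. Two common forms of the two-sided exact test are shown, equal-tail (twice the smaller tail) and minimum-likelihood (the sum of all outcomes no more probable than the one observed).

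**Step 1: reproduce the stated power.** At a true sensitivity of 0.90, the probability of at least one miss among 25 is

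1 − 0.90^25 = 1 − 0.072 = 0.928.

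This matches the stated figure only if a single miss rejects the null. For one miss to be significant at 0.05 in a single tail, 1 − p0^25 ≤ 0.05, so p0 ≥ 0.95^(1/25) = 0.998. The equal-tail version needs p0 ≥ 0.975^(1/25) = 0.999. If two misses were needed, power would be 72.9%. The figure above 90% therefore implies a null near 100%, as if RT-PCR were the comparison and perfectly sensitive. That is neither 95% nor 80%.

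**Step 2: rejection region with a null of 95%.** With X ~ Binomial(25, 0.95):

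- P(X ≤ 21) = 0.034. The minimum-likelihood p-value at 21 is 0.034, and at 22 it is 0.127, so this test rejects at 21 or fewer detected.
- The equal-tail p-value at 21 is 2 × 0.034 = 0.068, and at 20 it is 2 × 0.0072 = 0.014, so this test rejects at 20 or fewer.
- Neither form can reject upward, because P(X = 25) = 0.95^25 = 0.277.

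**Step 3: chance of declaring a difference from 95%.**

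| True sensitivity | Equal-tail, P(X ≤ 20) | Minimum-likelihood, P(X ≤ 21) |
|---|---|---|
| 0.90 | 9.8% | 23.6% |
| 0.85 | 31.8% | 52.9% |
| 0.80 | 57.9% | 76.6% |

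About 279 true positives would be needed for 90% power to separate 0.90 from 0.95 (two-sided, alpha 0.05), against the 25 planned for.

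**Step 4: the same test with a null of 80%.** The equal-tail form rejects at 15 or fewer or at 25: 0.0173 + 0.0038 = 0.021. The minimum-likelihood form rejects at 15 or fewer or at 24 or more: 0.0173 + 0.0274 = 0.045. A test truly at 80% is thus declared different 2–5% of the time against a null of 80%, and 58–77% of the time against a null of 95%.

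**The case against.** A reader might infer that Hypothesis 2a tests an antigen assay against a 95% benchmark belonging to another kind of test, so that a product meeting the specification would probably be declared worse. The documents do not support that, for three reasons.

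- Section 13.2 does not name 95%. Its reference to the published value can be read as the published sensitivity of whichever product is chosen. On that reading the plan lacks a number but does not use a wrong one.
- The 80% is a minimum for selection, not an expected value. A product with published sensitivity of 95% or more also qualifies, and the source behind the figure in 3.2 cannot be seen from the documents. It is not shown that the figure belongs to a different test type, only that nothing ties it to the specified one.
- A finding of worse performance is more likely than not, under both forms of the exact test, only near the floor. At 85% the two forms give 32% and 53%.

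It is also fair to say that the Aim 1 and Aim 3 estimates do not use the null in 13.2. For those aims the problem is how the intervention is described.

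These points limit the benchmark argument. They do not resolve the conflict between label and specification, which stands within a single paragraph, nor do they supply the missing null or explain the power figure.

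**Conclusion.** The concern holds in limited form. The description of the index test contradicts itself, and this needs no calculation to establish. For Hypothesis 2a, the numeric null is unstated, the one cited sensitivity is not linked to the specified test, and the power statement fits only a null near 100%.

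The size is conditional. If the null is 95%, with 25 true positives and an assumed two-sided alpha of 0.05, power at 90% sensitivity is 10–24% where the plan states more than 90%, so a non-significant result would say little about comparability. A test truly at 80% would be called different 58–77% of the time, and one at 85% 32–53%. The ranges run from the equal-tail to the minimum-likelihood exact test. How far any of this applies depends on the product chosen and its own published sensitivity, which the documents do not give.

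**What to change.** 1. Reconcile the passages so that one index test is described in the same terms in the title, aims, hypotheses, section 2 (including Table 4), section 3.2 and the eventual conclusions. For Aims 1 and 3 this correction to the description of the intervention is all that is needed.
2. In 13.2, state the null as a number: the published controlled-setting sensitivity of the assay actually used, with its source, fixed before Aim 2 results are examined.
3. State alpha, sidedness and the form of the exact test.
4. Restate the power for that null with 25 true positives, replacing the present figure.

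The cost is rewording and one recalculation. The new power figure will be less favourable unless the null is close to 100%. No new data or procedures are required.
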